art Ages 1	Changes easily from one at-home activity to another.	2	1	0	DK	?
2	Says "thank you" when given something.	2	1	0	DK	3
3	Changes behavior depending on how well he or she knows another person (for example, acts differently with family member than with stranger, etc.).	2	1	0	DK	3
4	Chews with mouth closed.	2	1	0	DK	7
5	Says "please" when asking for something.	2	1	0	DK	7
6	Ends conversations appropriately (for example, says, "Good-bye"; "See you later"; etc.).	2	1	0	DK	?
7	Cleans or wipes face and hands during and/or after meals.	2	1	0	DK	?
8	Responds appropriately to reasonable changes in routine (for example, refrains from complaining, etc.).	2	1	0	DK	?
9	bumping into someone, etc.).	2	1	0	DK	?
10	Chooses not to taunt, tease, or bully.	2	1	0	DK	7
11	shakes hands, greets them, etc.).	2	1	0	DK	7
12	Changes voice level depending on location or situation (for example, in a library, during a movie or play, etc.).	2	1	0	DK	?
13		2	1	0	DK	3
14	Refrains from talking with food in mouth.	2	1	0	DK	?
15	Talks with others without interrupting or being rude.	2	1	0	DK	?
16	Accepts helpful suggestions or solutions from others.	2	1	0	DK	7
17	Controls anger or hurt feelings when plans change for reason(s) that cannot be helped (for example, bad weather, car trouble, etc.).	2	1	0	DK	?
18	Keeps secrets or confidences for longer than one day.	2	1	0	DK	?
19	Says he or she is sorry after making unintentional mistakes or errors in judgment (for example, when unintentionally leaving someone out of a game, etc.).	2	1	0	DK	?
20	Shows understanding that gentle teasing with family and friends can be a form of humor or affection.	2	1	0	DK	?
21		2	1	0	DK	?
22	Chooses to avoid dangerous or risky activities (for example, jumping off high places, picking up a hitchhiker, driving recklessly, etc.).	2	1	0	DK	?
23	Controls anger or hurt feelings when he or she does not get his or her way (for example, when not allowed to watch television or attend a party; when suggestion is rejected by friend or supervisor; etc.).	2	1	0	DK	3
24	meets that person; etc.).	2	1	0	DK	3
25	Stops or stays away from relationships or situations that are hurtful or dangerous (for example, being bullied or made fun of, being taken advantage of sexually or financially, etc.).	2	1	0	DK	?
26	Controls anger or hurt feelings due to constructive criticism (for example, correction of misbehavior, discussion of test score or grade, performance review, etc.).	2	1	0	DK	?
27	Keeps secrets or confidences for as long as needed.	2	1	0	DK	?
28	Thinks about what could happen before making decisions (for example, refrains from acting impulsively, thinks about important information, etc.).	2	1	0	DK	?
29	Is aware of potential danger and uses caution when encountering risky social situations (for example, binge drinking parties, Internet chat rooms, personal ads, etc.).	2	1	0	DK	3
30	Shows respect for co-workers (for example, does not distract or interrupt others who are working, is on time for meetings, etc.).	2	1	0	DK	?

EudraCT Number: 2015-004904-50

Protocol V3 20Sep16

Physical Activity Response Options: 2 = Usually, 1 = Sometimes or Partially, DK = Don't Know N/O = No Opportunity Circle "?" If You Have a Question **Using Large Muscles** 1 Holds head erect for at least 15 seconds when held upright in parent's 0 DK or caregiver's arms. 2 Sits supported (for example, in a chair, with pillows, etc.) for at least 1 minute. 0 DK 3 Sits without support for at least 1 minute. 0 DK 4 Creeps or moves on stomach across floor. 0 DK 5 Sits without support for at least 10 minutes. 2 0 DK 6 Raises self to sitting position and sits without support for at least 1 minute. 0 DK 7 Crawls at least 5 feet on hands and knees, without stomach touching floor. 0 DK 8 Pulls self to standing position. 2 0 DK 9 Crawls up stairs. 0 DK 10 Takes at least two steps. 0 DK 11 Stands alone for 1 to 3 minutes. 0 DK DK 12 Rolls ball while sitting. 2 0 13 Climbs on and off low objects (for example, chair, step stool, slide, etc.). 0 DK 14 Crawls down stairs. 0 DK 15 Stands for at least 5 minutes. DK 0 2 1 16 Walks across room; may be unsteady and fall occasionally. 0 DK 17 Throws ball. DK 2 0 0 DK 18 Walks to get around; does not need to hold on to anything. 19 Climbs on and off adult-sized chair. 0 DK 20 Runs without falling; may be awkward and uncoordinated. 2 0 DK 21 Walks up stairs, putting both feet on each step; may use railing. 2 0 DK 22 Kicks ball. 0 DK 23 Runs smoothly without falling. 0 DK DK 24 Walks down stairs, facing forward, putting both feet on each step; may use railing. 2 0 25 Jumps with both feet off floor. 2 0 DK 26 Throws ball of any size in specific direction. 2 0 DK 27 Catches beach ball-sized ball with both hands from a distance of 2 or 3 feet. 2 0 DK 0 DK 28 Walks up stairs, alternating feet; may use railing. 29 Pedals tricycle or other three-wheeled toy for at least 6 feet. 0 DK Scoring Tip: You may mark "N/O" for No Opportunity if the individual does not have a N/O tricycle or three-wheeled toy. However, if the individual has such a vehicle but does not ride it for any reason, including parent or caregiver does not think he or she is ready, mark "0." 30 Jumps or hops forward at least three times. 2 1 0 DK

for balance.

31 Hops on one foot at least once without falling; may hold on to something

0 DK

	onse	Options: 2 = Usually, 1 = Sometimes or Partially, 0 = Never, DK = Don't Kr	now	N/O =	No	Oppor	tunity
sing I	Lar	ge Muscles, continued					Circle * If You I a Ques
	32	Climbs on and off high objects (for example, jungle gym, 4-foot slide ladder, etc.).	2	1	0	DK	?
	33	Walks down stairs, alternating feet; may use railing.	2	1	0	DK	?
100	34	Runs smoothly, with changes in speed and direction.	2	1	0	DK	3
	35	Rides bicycle with training wheels for at least 10 feet.	2	1	0	DK	3
		Scoring Tip: You may mark "N/O" for No Opportunity if the individual does not have a bicycle. However, if the individual has a bike but does not ride it for any reason, including parent or caregiver does not think he or she is ready, mark "O."		N/O			
- 1	36	Catches beach ball-sized ball (from at least 6 feet away) with both hands.	2	1	0	DK	?
-	37	Hops forward on one foot with ease.	2	1	0	DK	3
	38	Skips at least 5 feet.	2	1	0	DK	3
	39	Catches tennis or baseball-sized ball (from at least 10 feet away), moving to catch it if necessary.	2	1	0	DK	3
100	40	Rides bicycle with no training wheels without falling.	2	1	0	DK	?
		Scoring Tip: You may mark "N/O" for No Opportunity if the individual does not have a bicycle. However, if the individual has a bike but does not ride it for any reason, including parent or caregiver does not think he or she is ready, mark "O."		N/O			
Ages -4	1	Reaches for toy or object.	2	1	0	DK	?
	2	Picks up small objects (no larger than 2 inches on any side); may use both hands.	2	- 4			
100	3	The state of the s		1	0	DK	3
100		Moves object from one hand to the other.	2	1	0	DK DK	3
	4	Moves object from one hand to the other. Squeezes squeaky toy or object.	2	opposit :		600 Mills	
3 444	4 5			1	0	DK	?
		Squeezes squeaky toy or object.	2	1	0	DK DK	3
_	5	Squeezes squeaky toy or object. Picks up small object with thumb and fingers.	2	1 1 1	0 0	DK DK DK	3. 3.
-	5	Squeezes squeaky toy or object. Picks up small object with thumb and fingers. Removes object (for example, a block or clothespin) from a container.	2 2 2	1 1 1 1	0 0 0 0	DK DK DK DK	3.
	5 6 7	Squeezes squeaky toy or object. Picks up small object with thumb and fingers. Removes object (for example, a block or clothespin) from a container. Puts object (for example, a block or clothespin) into a container.	2 2 2 2	1 1 1 1	0 0 0 0 0	DK DK DK DK DK	3. 3. 3. 3.
	5 6 7 8	Squeezes squeaky toy or object. Picks up small object with thumb and fingers. Removes object (for example, a block or clothespin) from a container. Puts object (for example, a block or clothespin) into a container. Turns pages of board, cloth, or paper book, one at a time.	2 2 2 2 2	1 1 1 1 1	0 0 0 0 0	DK DK DK DK DK DK	
t Ages	5 6 7 8 9	Squeezes squeaky toy or object. Picks up small object with thumb and fingers. Removes object (for example, a block or clothespin) from a container. Puts object (for example, a block or clothespin) into a container. Turns pages of board, cloth, or paper book, one at a time. Stacks at least four small blocks or other small objects; stack must not fall.	2 2 2 2 2 2	1 1 1 1 1 1 1	0 0 0 0 0 0	DK DK DK DK DK DK DK DK	? ? ?
	5 6 7 8 9 10	Squeezes squeaky toy or object. Picks up small object with thumb and fingers. Removes object (for example, a block or clothespin) from a container. Puts object (for example, a block or clothespin) into a container. Turns pages of board, cloth, or paper book, one at a time. Stacks at least four small blocks or other small objects; stack must not fall. Opens doors by turning doorknobs.	2 2 2 2 2 2 2 2	1 1 1 1 1 1 1	0 0 0 0 0 0	DK DK DK DK DK DK DK DK DK	? ? ?
t Ages	5 6 7 8 9 10 11	Squeezes squeaky toy or object. Picks up small object with thumb and fingers. Removes object (for example, a block or clothespin) from a container. Puts object (for example, a block or clothespin) into a container. Turns pages of board, cloth, or paper book, one at a time. Stacks at least four small blocks or other small objects; stack must not fall. Opens doors by turning doorknobs. Unwraps small objects (for example, gum or candy).	2 2 2 2 2 2 2 2 2 2	1 1 1 1 1 1 1	0 0 0 0 0 0 0	DK	3 3 3 3 3 3 3 3 3 3 3 3 3 3 3 3 3 3 3 3
	5 6 7 8 9 10 11 12 13	Squeezes squeaky toy or object. Picks up small object with thumb and fingers. Removes object (for example, a block or clothespin) from a container. Puts object (for example, a block or clothespin) into a container. Turns pages of board, cloth, or paper book, one at a time. Stacks at least four small blocks or other small objects; stack must not fall. Opens doors by turning doorknobs. Unwraps small objects (for example, gum or candy). Completes simple puzzle of at least two pieces or shapes.	2 2 2 2 2 2 2 2 2 2 2	1 1 1 1 1 1 1 1 1	0 0 0 0 0 0 0	DK	3 3 3 3 3 3 3 3 3 3 3 3 3 3 3 3 3 3 3 3
	5 6 7 8 9 10 11 12 13	Squeezes squeaky toy or object. Picks up small object with thumb and fingers. Removes object (for example, a block or clothespin) from a container. Puts object (for example, a block or clothespin) into a container. Turns pages of board, cloth, or paper book, one at a time. Stacks at least four small blocks or other small objects; stack must not fall. Opens doors by turning doorknobs. Unwraps small objects (for example, gum or candy). Completes simple puzzle of at least two pieces or shapes. Turns book or magazine pages one by one. Uses twisting hand-wrist motion (for example, winds up toy,	2 2 2 2 2 2 2 2 2 2 2 2 2 2 2 2 2 2 2	1 1 1 1 1 1 1 1 1	0 0 0 0 0 0 0	DK	2 2 3 3 3 3 3 4 3 3 3
	5 6 7 8 9 10 11 12 13	Squeezes squeaky toy or object. Picks up small object with thumb and fingers. Removes object (for example, a block or clothespin) from a container. Puts object (for example, a block or clothespin) into a container. Turns pages of board, cloth, or paper book, one at a time. Stacks at least four small blocks or other small objects; stack must not fall. Opens doors by turning doorknobs. Unwraps small objects (for example, gum or candy). Completes simple puzzle of at least two pieces or shapes. Turns book or magazine pages one by one. Uses twisting hand-wrist motion (for example, winds up toy, screws/unscrews lid of jar, etc.). Holds pencil in proper position (not with fist) for writing or drawing.	2 2 2 2 2 2 2 2 2 2 2 2 2 2 2 2 2 2 2	1 1 1 1 1 1 1 1 1 1 1 1 1 1 1 1 1 1 1 1	0 0 0 0 0 0 0 0	DK D	3 3 3 3 3 3 3 3 3 3 3 3 3 3 3 3 3 3 3 3
	5 6 7 8 9 10 11 12 13 14	Squeezes squeaky toy or object. Picks up small object with thumb and fingers. Removes object (for example, a block or clothespin) from a container. Puts object (for example, a block or clothespin) into a container. Turns pages of board, cloth, or paper book, one at a time. Stacks at least four small blocks or other small objects; stack must not fall. Opens doors by turning doorknobs. Unwraps small objects (for example, gum or candy). Completes simple puzzle of at least two pieces or shapes. Turns book or magazine pages one by one. Uses twisting hand-wrist motion (for example, winds up toy, screws/unscrews lid of jar, etc.). Holds pencil in proper position (not with fist) for writing or drawing.	2 2 2 2 2 2 2 2 2 2 2 2 2 2 2 2 2 2 2	1 1 1 1 1 1 1 1 1 1	0 0 0 0 0 0 0 0 0	DK D	

EudraCT Number: 2015-004904-50

Protocol V3 20Sep16

0

0 DK

0

DK

DK

?

?

N/O

2 1 0

1

N/O

Response	Options: 2 = Usually, 1 = Sometimes or Partially, 0 = Never, DK = Don't R	Cnow	N/O =	No (Oppor	tunity
sing Sm	all Muscles, continued					Circle "?" If You Have a Question
19	Glues or pastes two or more pieces together (for example, for art or science projects, etc.).	2	1	0	DK	3
20	Uses tape to hold things together (for example, torn page, art project, etc.).	2	1	0	DK	7
21	Draws more than one recognizable form (for example, person, house, tree, etc.). Scoring Tip: Mark a "2" if the individual draws two or more recognizable forms; mark a "1" if the individual draws one form; mark a "0" if the individual does not draw any recognizable forms.	2	1	0	DK	7
22	Makes recognizable letters or numbers.	2	1	0	DK	?
23	Draws circle freehand while looking at example.	2	1	0	DK	?
24	Uses scissors to cut across paper along a straight line.	2	1	0	DK	3
25	Colors simple shapes; colors inside the lines.	2	1	0	DK	3
26	Cuts out simple shapes (for example, circles, squares, rectangles, etc.).	2	1	0	DK	?
27	Uses eraser without tearing paper.	2	1	0	DK	3
28	Draws square freehand while looking at example.	2	1	0	DK	?
29	Draws triangle freehand while looking at example.	2	1	0	DK	3
30	Ties knot.	2	1	0	DK	?
31	Draws straight line using a ruler or straightedge.	2	1	0	DK	?
32	Unlocks dead-bolt, key, or combination locks that require twisting.	2	1	0	DK	3
	Scoring Tip: You may mark "N/O" for No Opportunity if there are no dead-bolt, key, or combination locks in the home.		N/O			
7.7.7.7.0.00		- 65122	Circo organi	Charles Co.	Name of Street	N 35

33 Cuts out complex shapes (for example, stars, animals, alphabet letters, etc.).

Scoring Tip: You may mark "N/O" for No Opportunity if there is no computer in the home.

Scoring Tip: You may mark "N/O" for No Opportunity if there is no computer in the home.

34 Uses keyboard, typewriter, or touch screen to type name or short words;

36 Uses a keyboard to type up to 10 lines; may look at the keys.

may look at keys.

35 Ties secure bow.

Physical Activity, continued

Protocol V3 20Sep16

Problem Behaviors Part 1

Section	n A					Circle "?" If You Hav
Start Ages		Is overly dependent (that is, clings to caregiver, teacher, brother, or sister).	0	1	2	a Question
3+						
		Avoids others and prefers to be alone.	0	1	2	3
	3	Has eating difficulties (for example, eats too fast or too slowly, hoards food, overeats, refuses to eat, etc.).	0	1	2	1
	4	Has sleep difficulties (for example, sleepwalks, has frequent nightmares, sleeps significantly more or less than typical for his or her age).	0	1	2	?
	5	Refuses to go to school or work because of fear, feelings of rejection or isolation, etc.	0	1	2	3
	6	Is overly anxious or nervous.	0	1	2	7
	7	Cries or laughs too easily.	0	1	2	7
	8	Has poor eye contact (that is, does not look at or face others when speaking or spoken to).	0	1	2	?
	9	Is sad for no clear reason.	0	1	2	3
	10	Avoids social interaction.	0	1	2	3
	11	Lacks energy or interest in life.	0	1	2	?
3+					17.50	
Start Ages	1	Is impulsive (that is, acts without thinking).	0	1	2	a Question
3+		3,000				
	2	Has temper tantrums.	0	1	2	?
			0	1	2	7
		Has temper tantrums.		100		177
	3 4	Has temper tantrums. Intentionally disobeys and defies those in authority.	0	1	2	7
	3 4 5	Has temper tantrums. Intentionally disobeys and defies those in authority. Taunts, teases, or bullies.	0	1	2	?
	3 4 5 6	Has temper tantrums. Intentionally disobeys and defies those in authority. Taunts, teases, or bullies. Is inconsiderate or insensitive to others.	0 0	1 1 1	2 2 2	7
	3 4 5 6 7	Has temper tantrums. Intentionally disobeys and defies those in authority. Taunts, teases, or bullies. Is inconsiderate or insensitive to others. Lies, cheats, or steals.	0 0 0	1 1 1 1	2 2 2 2	3. 3.
	3 4 5 6 7 8	Has temper tantrums. Intentionally disobeys and defies those in authority. Taunts, teases, or bullies. Is inconsiderate or insensitive to others. Lies, cheats, or steals. Is physically aggressive (for example, hits, kicks, bites, etc.).	0 0 0 0	1 1 1 1 1	2 2 2 2 2	3. 3.
	3 4 5 6 7 8	Has temper tantrums. Intentionally disobeys and defies those in authority. Taunts, teases, or bullies. Is inconsiderate or insensitive to others. Lies, cheats, or steals. Is physically aggressive (for example, hits, kicks, bites, etc.). Is stubborn or sullen. Says embarrassing things or asks embarrassing questions in public (for example, "You're fat," or "What's that big red thing on your nose?").	0 0 0 0 0 0 0	1 1 1 1 1 1 1	2 2 2 2 2 2 2 2	3 3 4 5 5 6 6 6 6 6 6 6 6 6 6 6 6 6 6 6 6 6
3 3 3 3 3 3 3 3 3 3 3 3 3 3 3 3 3 3 3 3	3 4 5 6 7 8 9	Has temper tantrums. Intentionally disobeys and defies those in authority. Taunts, teases, or bullies. Is inconsiderate or insensitive to others. Lies, cheats, or steals. Is physically aggressive (for example, hits, kicks, bites, etc.). Is stubborn or sullen. Says embarrassing things or asks embarrassing questions in public (for example,	0 0 0 0 0	1 1 1 1 1	2 2 2 2 2 2 2	? ? ? ? ? ? ?
	3 4 5 6 7 8 9	Has temper tantrums. Intentionally disobeys and defies those in authority. Taunts, teases, or bullies. Is inconsiderate or insensitive to others. Lies, cheats, or steals. Is physically aggressive (for example, hits, kicks, bites, etc.). Is stubborn or sullen. Says embarrassing things or asks embarrassing questions in public (for example, "You're fat," or "What's that big red thing on your nose?").	0 0 0 0 0 0 0	1 1 1 1 1 1 1	2 2 2 2 2 2 2 2	? ? ? ? ? ? Circle "?"
	3 4 5 6 7 8 9	Has temper tantrums. Intentionally disobeys and defies those in authority. Taunts, teases, or bullies. Is inconsiderate or insensitive to others. Lies, cheats, or steals. Is physically aggressive (for example, hits, kicks, bites, etc.). Is stubborn or sullen. Says embarrassing things or asks embarrassing questions in public (for example, "You're fat," or "What's that big red thing on your nose?").	0 0 0 0 0 0 0	1 1 1 1 1 1 1	2 2 2 2 2 2 2 2	? ? ? ? ? ? Circle "?"
Start Ages	3 4 5 6 7 8 9 10	Has temper tantrums. Intentionally disobeys and defies those in authority. Taunts, teases, or bullies. Is inconsiderate or insensitive to others. Lies, cheats, or steals. Is physically aggressive (for example, hits, kicks, bites, etc.). Is stubborn or sullen. Says embarrassing things or asks embarrassing questions in public (for example, "You're fat," or "What's that big red thing on your nose?"). Behaves inappropriately at the urging of others.	0 0 0 0 0 0 0	1 1 1 1 1 1 1 1	2 2 2 2 2 2 2 2 2	? ? ? ? ? ? Circle "?" If You Han a Questio
Start Ages	3 4 5 6 7 8 9 10 11 2	Has temper tantrums. Intentionally disobeys and defies those in authority. Taunts, teases, or bullies. Is inconsiderate or insensitive to others. Lies, cheats, or steals. Is physically aggressive (for example, hits, kicks, bites, etc.). Is stubborn or sullen. Says embarrassing things or asks embarrassing questions in public (for example, "You're fat," or "What's that big red thing on your nose?"). Behaves inappropriately at the urging of others.	0 0 0 0 0 0 0 0 0	1 1 1 1 1 1 1 1 1	2 2 2 2 2 2 2 2 2 2 2 2	? ? ? ? Circle "?" If You Han a Questio
Section Start Ages 3+	3 4 5 6 7 8 9 10 11 2	Has temper tantrums. Intentionally disobeys and defies those in authority. Taunts, teases, or bullies. Is inconsiderate or insensitive to others. Lies, cheats, or steals. Is physically aggressive (for example, hits, kicks, bites, etc.). Is stubborn or sullen. Says embarrassing things or asks embarrassing questions in public (for example, "You're fat," or "What's that big red thing on your nose?"). Behaves inappropriately at the urging of others. Sucks thumb or fingers. Wets bed or must wear diapers at night.	0 0 0 0 0 0 0 0 0 0 0 0 0 0 0 0 0 0 0 0	1 1 1 1 1 1 1 1 1 1	2 2 2 2 2 2 2 2 2 2 2 2 2 2 2 2 2 2 2 2	? ? ? ? Circle "?" If You Has a Questio

Protocol V3 20Sep16

Problem Behaviors Part 1, continued

Response Options: 2 = Often, 1 = Sometimes, 0 = Never				
Section C, continued				Circle "?" If You Have a Question
6 Grinds teeth during the day or night.	0	1	2	3
7 Has a hard time paying attention,	0	1	2	?
8 Is more active or restless than others of same age.	0	1	2	?
9 Uses school or work property (for example, telephone, Internet access, office supplies, etc.) for unapproved personal purposes.	0	1	2	?
10 Swears.	0	1	2	7
11 Runs away (that is, is missing for 24 hours or longer).	0	1	2	?
12 Is truant from school or work.	0	1	2	3
13 Ignores or doesn't pay attention to others around him or her.	0	1	2	7
14 Uses money or gifts to "buy" affection.	0	1	2	7
15 Uses alcohol or illegal drugs during the school or work day.	0	1	2	1

Problem Behaviors Part 2

Sectio	n D	Response Options: 2 = Often, 1 = Sometimes, 0 = Never, 5 = Severe,	M =	,,,,,	acia.			Circle "?" If You Have a Question
Start Ages 3+	1	Engages in inappropriate sexual behavior (for example, exposes self, masturbates in public, makes improper sexual advances, etc.).	0	1	2	S	M	?
	2	Is obsessed with objects or activities (for example, constantly repeats words or phrases, is preoccupied with mechanical objects, etc.).	0	1	2	S	M	3
	3	Expresses thoughts that do not make sense (for example, talks about hearing voices, seems delusional, etc.).	0	1	2	S	M	3
	4	Has strange habits or ways (for example, makes repetitive noises, odd hand movements, etc.).	0	1	2	S	M	3
	5	Consistently prefers objects to people (for example, pays more attention to objects than to people, etc.).	0	1	2	S	M	
37	6	Displays behaviors that cause injury to self (for example, bangs head, hits or bites self, tears at skin, etc.).	0	1	2	S	M	3
	7	Destroys own or another's possessions on purpose.	0	1	2	S	М	3
	8	Uses bizarre speech (for example, has conversations with self in public, speaks in phrases or sentences that have no meaning, repeats same word or phrase over and over, etc.).	0	1	2	S	М	3
	9	Is unaware of what is happening around him or her (for example, seems to be in a "fog," stares blankly, etc.).	0	1	2	S	M	?
	10	Rocks back and forth repeatedly.	0	1	2	S	М	?
	11	Is unusually fearful of ordinary sounds, objects, or situations.	0	1	2	S	М	?
	12	Remembers odd information in detail years later.	0	1	2	S	М	?
2	13	Is unable to complete a normal school or work day because of chronic pain or fatigue.	0	1	2	S	M	3
	14	Is unable to complete a normal school or work day because of psychological symptoms.	0	1	2	S	М	3

EudraCT Number: 2015-004904-50 Protocol Amendment 2, V2 18Oct16

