9.2.12.3 Vineland Adaptive Behavior Scales, Second Edition

The Vineland-II⁵⁵ is an individually administered instrument for assessing adaptive behaviors and is widely used in pediatric clinical trials due to its applicability to children of all ages and developmental levels. The Vineland-II will be completed by the caregiver using a rating scale. Due to the possibility of cognitive/developmental delay, caregivers should start the assessment at the lowest age, irrespective of the patient's actual age.

EudraCT Number: 2015-004904-50

Protocol V3 20Sep16

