- If you have never seen the individual perform a behavior and don't know whether he or she performs it, circle "DK" for Don't Know.
- If an item has a Scoring Tip, use the tip to help you decide which response option to circle.
- If an item has a Scoring Tip that says you may circle "N/O" for No Opportunity, you may circle that option, if appropriate, instead of a "2," "1," "0," or "DK."
- Some sections do not apply to children younger than 3 years of age. If the child
 you are rating is younger than the age of the first start point, do not mark any items
 in that section.

Here is an example:

Continued on next page

2

EudraCT Number: 2015-004904-50

Protocol V3 20Sep16

Directions continued

If you want to change a response, mark an X through it, and circle your new choice.

If you have a question about any item, first mark the response that best describes the individual's behavior, and then circle the question mark (?) to the right of the response options.

Use the following table to help you choose the response that best describes the behavior of the individual you are rating.

RATING	THE INDIVIDUAL:
2 Usually	Usually performs the behavior without help or reminders when it is needed; or Performed the behavior at a younger age but now has outgrown it
1 Sometimes or Partially	Sometimes performs the behavior without help or reminders when it is needed; or Sometimes does it without help but sometimes needs help; or Sometimes does it without help but needs reminders; or Performs part of the behavior without help or reminders
0 Never	Never performs the behavior without help or reminders; or Never performs the behavior, because he or she is unable; or Never performs the behavior, because he or she is too young; or Never performs the behavior, because he or she is not allowed to; or Never performs the behavior, because he or she has a physical disability that prevents the behavior

Remember to respond in each section to every item after the start point for the individual's age.

EudraCT Number: 2015-004904-50

Protocol V3 20Sep16

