38	Travels at least 5 to 10 miles to unfamiliar destination (that is, bikes, uses public transportation, or drives self).	2	1	0	DK	?
39	Earns money at part-time job (that is, at least 10 hours a week) for 1 year. Scoring Tip: Do not mark 1.	2	X	0	DK	?
40	Attempts to improve job performance after receiving constructive criticism from supervisor.	2	1	0	DK	?
	Scoring Tip: You may mark "N/O" for No Opportunity If the individual has not held a job.		N/O			
41	Manages own money (for example, pays most or all own expenses, uses checks or money orders for purchases as needed, etc.).	2	1	0	DK	?
42	Has held full-time job for 1 year.	2	X	0	DK	3
	Scoring Tip: Do not mark 1.					
43	Budgets for monthly expenses (for example, utilities, rent, etc.).	2	1	0	DK	?
44	Applies for and uses personal credit card responsibly (for example, does not exceed credit limit, pays on time, etc.).	2	1	0	DK	7

Protocol V3 20Sep16

Social Skills and Relationships

elati	ng t	Response Options: 2 = Usually, 1 = Sometimes or Partially, 0 = Never, 1 O Others	DK = Do				Circle f If You I a Ques
art Ages 0-4	1	Looks at face of parent or caregiver.	2	1	0	DK	3
0-4	2	Watches (that is, follows with eyes) someone moving by crib or bed for 5 seconds or more.	2	1	0	DK	3
	3	Shows two or more emotions (for example, laughs, cries, screams, etc.).	2	1	0	DK	3
3	4	Smiles or makes sounds when approached by a familiar person.	2	1	0	DK	?
	5	Makes or tries to make social contact (for example, smiles, makes noises, etc.).	2	1	0	DK	3
	6	Reaches for familiar person when person holds out arms to him or her.	2	1	0	DK	3
	7	Shows preference for certain people and objects (for example, smiles, reaches for or moves toward person or object, etc.).	2	1	0	DK	3
	8	Shows affection to familiar persons (for example, touches, hugs, kisses, cuddles, etc.).	2	1	0	DK	3
	9	Imitates or tries to imitate parent's or caregiver's facial expressions (for example, smiles, frowns, etc.).	2	1	0	DK	1
- 7	10	Moves about looking for parent or caregiver or other familiar person nearby.	2	1	0	DK	1
	11	Shows interest in children the same age, other than brothers or sisters (for example, watches them, smiles at them, etc.).	2	1	0	DK	1
5-15	12	Imitates simple movements (for example, claps hands, waves good-bye, etc.).	2	1	0	DK	
	13	Uses actions to show happiness or concern for others (for example, hugs, pats arm, holds hands, etc.).	2	1	0	DK	

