4.7.3.4. Vineland Adaptive Behavior Scales, Second Edition (Vineland-II)

The Vineland-II is an individually administered instrument for assessing adaptive behaviors and is widely used in pediatric clinical trials due to its applicability to children of all ages and developmental levels. The Vineland-II will be completed by the caregiver using a rating scale. Due to the possibility of cognitive/developmental delay, caregivers should start the assessment at the lowest age, irrespective of the patient's actual age. The Vineland-II consists of 5 domains (communication, daily living skills, socialization, motor skills, and maladaptive behavior) with items that are rated as 0=Never, 1=Sometimes or Partially, or 2=Usually. The Vineland-II scores will be calculated as the sum of all individual item scores across all scales.

Observed and change from baseline in Vineland-II scores will be summarized descriptively by visit for the OLE phase only.

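### The SAP's Vineland-II total adds Problem Behaviors items, where higher is worse, to adaptive items, where higher is better; any such item that is marked moves the score the wrong way

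*Protocol*

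**What the plan says.** SAP 4.7.3.4 ends its list of five Vineland-II domains with "and maladaptive behavior) with items that are rated as 0=Never, 1=Sometimes or Partially, or 2=Usually". It then gives the scoring rule: "The Vineland-II scores will be calculated as the sum of all individual item scores across all scales". Observed values and change from baseline are summarized descriptively by visit, for the extension only (planned Table 9.3). The SAP has no reverse coding and no separate maladaptive score.

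The form in Protocol Appendix 3.3 uses two keys. In the adaptive sections, 2 means that the child usually performs a skill. In Problem Behaviors Part 1 the key is "Response Options: 2 = Often, 1 = Sometimes, 0 = Never", applied to undesirable behaviors. Part 2 (Section D) uses the same three levels and adds the letter codes S and M.

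Two instructions govern which sections are completed:

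- The form's directions state: "Some sections do not apply to children younger than 3 years of age". A section whose first start point is above the child's age is to be left unmarked. Every Problem Behaviors section starts at 3+.
- Protocol 9.2.12.3, repeated in the SAP, says that because of possible developmental delay "caregivers should start the assessment at the lowest age, irrespective of the" child's real age. It does not mention the sections that begin at age 3.

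**The concern.** A total is interpretable only if all its items point the same way. Here one block points the other way, and the SAP's single rating key hides this.

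The clash shows at item level. "Looks at face of parent or caregiver" is an adaptive item, and an infant who gains eye contact scores up on it. "Has poor eye contact (that is, does not look at or face others when speaking or spoken to" is a Problem Behaviors item, and the same gain scores down on it. In the other direction, "Has sleep difficulties (for example, sleepwalks, has frequent nightmares, sleeps significantly more or less than typical for his or her age" adds points as sleep gets worse, as do the neighboring items on eating and on energy. Protocol 3.2 reports somnolence (23%), fatigue (17%) and decreased appetite (17%) among the drug's most common adverse events. Those rates come from adults and children in a compassionate-use program and not from infants, so they show only that such items are relevant.

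Table 9.3 is the only planned table for the Vineland-II, and so for the part of the extension objective that concerns adaptive behavior and development. A change that mixes directions could be read as developmental gain or as lack of it.

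**Working it through.** The documents give no power, effect size or standard deviation for this endpoint, so there is no figure to reproduce. Three checks apply.

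**1. How much of the form runs the other way.** Items are counted by the last printed number in each section of Appendix 3.3.

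| Block | Items | Maximum points |
|---|---|---|
| Communication | 20 + 54 + 25 = 99 | 198 |
| Daily living | 41 + 24 + 44 = 109 | 218 |
| Social | 38 + 31 + 30 = 99 | 198 |
| Physical activity | 40 + 36 = 76 | 152 |
| **Adaptive total** | **383** | **766** |
| Problem Behaviors A to D | 11 + 10 + 15 + 14 = **50** | **100** |

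The share is 100 / (766 + 100) = 100 / 866 = 11.5% of the maximum.

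**2. Who could have these items marked under the form's own rule.** Inputs: age at consent at most 24 months inclusive (Protocol 6.1.1); Vineland-II at Visit 2, Visit 10 (Day 211 ±7), Visit 12 (Day 379 ±7) or withdrawal. Assumptions: 1 to 10 days from consent to Visit 2, and 30.4375 days per month. The phrase 24 months inclusive is read either as exactly 24 or as up to the 25-month birthday.

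Age at visit = age at consent + (days from consent to Visit 2 + study day − 1) / 30.4375.

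- Visit 2, oldest child: 24.0 to 25.3 months.
- Visit 10 at the late end of its window (Day 218), oldest child: 31.2 to 32.5 months.
- Visit 12, oldest child: 36.5 to 38.0 months.

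The lowest consent age that reaches 36 months by Visit 12 is:

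- 36 − (1 + 378) / 30.4375 = 23.55 months with the shortest gap and nominal Day 379;
- 36 − (10 + 385) / 30.4375 = 23.02 months with the longest gap and Day 386.

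So if caregivers follow the form, no child has Problem Behaviors points at baseline or Visit 10. Only a child aged about 23 months or more at consent can have them at Visit 12, and then with no baseline counterpart.

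**3. What the sum does when the items are marked.** Change in SAP total = adaptive change + problem change. The changes below are assumed for illustration.

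| Adaptive | Problem items | SAP total | Adaptive only |
|---|---|---|---|
| +10 | −10 (better) | 0 | +10 |
| +10 | 0 or blank | +10 | +10 |
| +10 | +10 (worse) | +20 | +10 |
| +10 | −20 (better) | −10 | +10 |

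For the eye-contact pair, +2 on the adaptive item and −2 on the problem item give 0. If one child moves from 0 to 2 on the sleep, eating and energy items, the problem block adds 3 × 2 = 6 points. Across 9 children that shifts the mean change by 6 / 9 = 0.67 points, and by more if fewer contribute. This counts the problem block only. A sedated infant might also lose adaptive points, so it is not a net change.

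**The case against.** The strongest reply is that the form itself prevents the problem. Its Problem Behaviors sections have a single start point, 3+, and younger children are to be left unmarked there. The lowest-age instruction is most naturally read as moving the starting point down within a section that offers several, and neither document says that it overrides the form. For nearly every infant the section would then be blank, and the SAP total would equal the adaptive total. This stands, and it limits the point.

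It does not remove the point. The form also tells respondents to answer every item after the start point in each section. A caregiver told to ignore the child's age can reasonably read the two together as covering the 3+ sections, and the SAP itself lists the domain as part of the score. Caregivers may also differ, or change between visits. SAP 4.2.8 in general makes no substitutions for missing data, so a section marked at one visit and blank at another produces a false change.

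It is also fair to say that the stakes are modest. The endpoint is secondary and descriptive, no test or sample size depends on it, and Listing 8.2 shows Vineland-II data by patient. The form's response key is correct as printed; the fault lies in the SAP's scoring sentence and rating labels.

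A reader might infer that real improvement is being cancelled or reversed in this trial, or that 11.5% of the score is in error. The documents support neither. Cancellation requires the section to be marked, which the form discourages at these ages. The 100 points include items on truancy and on alcohol or drug use at school or work, which infants cannot score.

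**Conclusion.** The scoring rule in SAP 4.7.3.4 is wrong as written. It adds items of opposite direction without reversal and labels the Problem Behaviors items with the adaptive key. It also has no numeric rule for the S and M codes in Section D. Every marked problem-behavior point above zero raises a score that otherwise rises with better function.

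The effect on results is conditional. It is nil for nearly all infants if the form's age rule was followed. It is real in two situations: caregivers completed the 3+ sections under the lowest-age instruction, or a child aged about 23.0 to 23.6 months or more at consent had turned 3 by Visit 12. The documents do not show how often either occurred, so the expected error cannot be stated. The 100-point figure is only the form's upper limit.

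The affected summary covers at most the 9 pilot patients of SAP 4.1, and fewer if some did not enter the extension or lack Vineland-II data. The change should be made because it is right under either reading of the completion rule. It affects no inferential result.

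**What to change.** In SAP 4.7.3.4, replace the scoring sentence with wording such as:

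> The Vineland-II adaptive score is computed from the communication, daily living, socialization and motor items only. Problem Behaviors items (Parts 1 and 2) are never added to it. Where they are marked, they are summarized separately by visit, with higher values meaning worse behavior; the S and M codes in Section D are not summed.

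Correct the sentence that gives one rating key for all five domains, so that Problem Behaviors carries the form's Never / Sometimes / Often key. Split Table 9.3 into an adaptive block and a problem-behavior block, showing in the second how many children had the section marked at each visit.

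The cost is SAP text and one extra table block. It needs no new data, no protocol amendment and no change at sites.
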